### **Multiple comparisons and multiplicity**

No formal method will be used to account for multiple comparisons. All comparisons will be defined within this document *a-priori* and all will be reported.

### **Method for handling non-adherence**

Analysis of all primary and secondary outcomes will be performed on an intention-to-treat basis. A Complier Average Causal Effect (CACE) analysis and per protocol analysis will also be conducted for the primary analysis.

## **Method for handling time-varying interventions**

Not applicable

## **Method for handling outliers and influential points**

Where any outliers are identified they will be investigated to determine whether they are true recorded values or a data entry error. Where outliers are identified as a true recorded value, an assessment will be made as to whether there are clear quality indications to remove them. If such indications exist, the outliers will be removed. If such indications do not exist, the analysis will be performed both including and excluding the outlier to assess the robustness of the conclusions.

## **Data from external sources**

Not applicable

## **Derived and computed variables**

All derived and computed variables will be documented in the analysis programmes. The primary outcome is a summation of all types of medical attendances across the entire trial, for each participant.

The primary outcome, and the breakdown of unscheduled medical opinion, will be taken solely from the phone call data as this data has been confirmed against clinical records.

Medication use data may be recorded on either the phone call CRF and/or the diary card. A medication will be defined as being used if it appears in either of these two records.

Medical attendance data was collected strictly within 12 months, as calculated from the date of randomisation. Participants who do not experience an event are censored at exactly 12 months of follow up or the point of withdrawal from follow up. Any diary data collected outside of the 12 month follow up will be excluded from the analysis. Participants who do not experience episodes of cold or wheeze will be censored at the point of 12 months from randomisation or withdrawal from medication, as diary cards are not completed for those not taking IMP.

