## **STUDY OBJECTIVES AND ENDPOINTS**

### **Study objectives**

#### **Primary objectives**

1.To determine whether intermittent treatment with oral montelukast in preschool children reduces the need for unscheduled medical attention (GP visit, hospital attendance, hospital admission) for wheeze.

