### **Outcome measures**

#### **Primary outcomes**

The number of times a child attends for an unscheduled medical opinion (a summation of hospital admissions, attendances, GP visits,) with respiratory problems over a 12 month period as confirmed from clinical records

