#### **Secondary outcomes**

#### **Breakdown of unscheduled medical opinion**

Hospital admissions:

- Number of hospital admissions over the 12 month period as recorded at each phone call
- Duration of hospital admissions as recorded at each phone call
- Time from randomisation date to date of first hospital admission as recorded at each phone call

Hospital admission for wheeze:

- Number of hospital admissions over the 12 month period as recorded at each phone call
- Time from randomisation date to date of first hospital admission as recorded at each phone call

Hospital attendance for wheeze:

- Number of hospital attendances (A&E) over the 12 month period as recorded at each phone call
- Time from randomisation date to date of first hospital attendance (A&E) as recorded at each phone call

Unscheduled GP visit for wheeze:

- Number of unscheduled GP visits over the 12 month period as recorded at each phone call
- Time from randomisation date to date of first unscheduled GP visit as recorded at each phone call

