### **Follow up**

#### ***Unscheduled medical attendance***

Phone call data: Type of attendance (A&E; Hospital; GP; Pharmacist; Other)

Phone call data: Duration of visit (calculated from date of admission and date of discharge)

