## **ANALYSIS OF PRIMARY OUTCOME**

### **Definition of outcome measure**

The primary outcome for each participant is the total number of unscheduled medical attendances over the course of the trial.

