**Table 3 Primary analysis: unscheduled medical attendances for wheeze over 12 months**

ITT population	Montelukast N=	Placebo N=	Adjusted IRR (95% CI) 	p-value
Follow up time (days)				
Number of :				
Any medical attendance				
All				
Stratum A				
Stratum B				
Stratum 5/5 and 5/x				
Stratum D x/x				

ICS at baseline  
Multitrigger vs episodic wheeze

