**Hospital admissions**  
**Hospital attendances (A&E or admission)**  
**Unscheduled GP visits**

**Parents considered medication to be efficacious, N(%)**

---

Data are mean (SD)

 Data are analysed using Poisson regression with fixed effects for stratification factor and treatment group a random effect for individual to account for overdispersion with follow up time fitted as the exposure. An interaction term has been included to assess whether there is a differential treatment effect dependent on stratum.

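### The SAP gives the primary outcome three different causes (wheeze, respiratory problems, none stated), so the primary count depends on which section is programmed

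*SAP*

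**What the plan says.** The cause of attendance appears in three forms.

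- **Wheeze.** The primary objective asks whether treatment "reduces the need for unscheduled medical attention (GP visit, hospital attendance, hospital admission) for wheeze". The title of Table 3, which reports the primary analysis, reads "unscheduled medical attendances for wheeze over 12 months".
- **Respiratory problems.** The Primary outcomes section sums admissions, attendances and GP visits "with respiratory problems over a 12 month period as confirmed from clinical records".
- **No cause.** Derived and computed variables says "The primary outcome is a summation of all types of medical attendances across the entire trial, for each participant". The definition of the outcome measure, under both the primary analysis and the subgroup analyses, is "the total number of unscheduled medical attendances over the course of the trial".

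Two related passages bear on what is summed. The derivation section takes the outcome only from phone call data, and the phone call field under Follow up is "Type of attendance (A&E; Hospital; GP; Pharmacist; Other". The secondary outcomes have "Number of hospital attendances (A&E) over the 12 month period as recorded at each phone call", whereas the row in Table 3 is "Hospital attendances (A&E or admission"; Table 5 uses the same wider label.

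**The concern.** The primary outcome should lead any programmer to the same count. Here a reader of the objective keeps wheeze contacts only, a reader of the outcome section keeps all respiratory contacts, and a reader of the derivation rule alone applies no cause filter.

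The SAP itself treats cause as something that changes a count. The secondary outcomes list hospital admissions and, separately, hospital admissions for wheeze. Colds are also recorded apart from wheeze.

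The SAP says that the analysis will be run unblinded, that one person writes and runs the code, and that derivations will be documented in the analysis programmes. The choice of definition would then be made by someone who knows the allocation. None of the planned sensitivity analyses compares the definitions.

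**Working it through.** **1. The passages side by side**

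| SAP section | Cause | Types |
|---|---|---|
| Primary objectives | wheeze | GP, hospital attendance, admission |
| Primary outcomes | respiratory problems | admission, attendance, GP |
| Derived and computed variables | none | all types |
| Analysis of primary outcome, definition | none | not listed |
| Subgroup analyses, definition | none | not listed |
| Table 3 title | wheeze | not listed |

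Wheeze and respiratory problems are both stated outright, and they conflict. The three sections without a cause do not resolve it. The time window is not a further conflict: the derivation section limits attendance data to 12 months from randomisation.

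**2. Does the sample size section show which cause was meant?**

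Inputs (Sample size determination): control mean 0.76, SD 1.22, treated mean 0.51, 90% power, two-sided 5%, 6% loss, 1050 children.

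- Per arm: 2 × (1.960 + 1.282)² × 1.22² / 0.25² = 500.5, so 501.
- Total: 1002. Divided by 0.94: 1066.

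This is within 2% of 1050, which the SAP obtained by simulation, so the figure is reproduced. It does not settle the cause, because 0.76 is a mean number of oral steroid courses used as a proxy for episodes.

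**3. Illustration of what the choice could do to the rate ratio**

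Assumptions, none of them from the SAP: the planned 33% drop applies to wheeze attendances; 0.76 is the control wheeze mean; a share f of the control-arm count is other contacts, wholly unaffected by treatment; dispersion k stays constant.

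- IRR = 0.67 × (1 − f) + f
- k = (1.22² − 0.76) / 0.76² = 1.261
- m0 = 0.76 / (1 − f); m1 = m0 × IRR
- Evaluable: 1300 × 0.94 = 1222, or 611 per arm
- SE(log IRR) = √[(1/m0 + 1/m1 + 2k) / 611]
- Power = Φ(|log IRR| / SE − 1.96)

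| f | IRR | m0 | m1 | SE | Power |
|---|---|---|---|---|---|
| 0 | 0.67 | 0.760 | 0.509 | 0.097 | 98% |
| 20% | 0.736 | 0.950 | 0.699 | 0.091 | 92% |
| 40% | 0.802 | 1.267 | 1.016 | 0.084 | 75% |

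A second approximation uses 1050 children less 6% and a quasi-Poisson variance factor held at 1.22² / 0.76 = 1.96. Power is then about 94%, 87% and 75% at the same shares.

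**4. Illustration for an A&E visit that ends in admission**

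Assume admissions are 20% of events with IRR 1.0 and all other events have IRR 0.67.

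- Counted once: 0.8 × 0.67 + 0.2 × 1.0 = 0.736.
- Counted twice: (0.8 × 0.67 + 0.4 × 1.0) / 1.2 = 0.780.

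If all types share one IRR, counting admissions twice leaves it unchanged, though the event total still changes.

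**The case against.** The strongest reply is that the SAP has one full definition, under Primary outcomes, with types, cause, window and source together. On that view the sections without a cause are shorthand. This is fair for those sections: nothing in them shows that non-respiratory attendances were meant to count. It does not remove the clash with the objective and with the title of the primary results table.

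A reader might draw four stronger conclusions that the SAP does not support.

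- **Pharmacist and Other contacts are in the primary outcome.** The objective, the fourth objective in the SAP's list, the outcome section and both secondary analysis lists name the same three types. The phone call field shows what was collected and defines no endpoint. The derivation rule is loosely worded, no more.
- **Every admission is counted twice.** The wider label belongs to a secondary row in Tables 3 and 5. The primary outcome has its own row, and nothing says it is the sum of the rows below. A&E and Hospital are separate values of one field. What remains is the missing rule for an A&E visit that becomes an admission.
- **Power is lost.** The shares are invented for illustration. At 20%, power in the 1300-child calculation is still above the planned 90%. The SAP also reports 1347 participants, more than 1300.
- **Wheeze is the right cause.** The SAP does not settle this. It cites protocol version 7, which was not available for this review.

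**Conclusion.** The inconsistency in cause is established from the text and concerns the primary endpoint, so it should be resolved before unblinding. The count depends on the section followed. The expected rate ratio depends on it only if the treatment effect differs by cause. The SAP gives no breakdown of attendances by cause or type, so the size of any shift is unknown; the range from 0.67 to 0.80 rests wholly on the stated assumptions.

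The loose wording on types, the mismatch in the hospital attendance label and the missing A&E-to-admission rule are secondary points that need clarifying. They are not evidence of a wrong count.

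**What to change.** Before unblinding:

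1. Take the cause, wheeze or respiratory problems, from the approved protocol. Use it in the primary objective, Primary outcomes, Derived and computed variables, both outcome definitions (primary and subgroup) and Table 3.
2. In the derivation rule, limit the count to unscheduled GP visits, A&E attendances and hospital admissions, and exclude Pharmacist and Other.
3. Count an A&E visit that leads to admission as one event in the primary total.
4. Align the hospital attendance label in Tables 3 and 5 with the A&E definition in the secondary outcomes.
5. Report the other cause definition as a sensitivity analysis if cause was recorded.

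The cost is SAP wording and one derivation rule. Type of attendance is already collected. Whether cause is available is not shown: the phone call list under Follow up has no cause field, although the wheeze-specific secondary outcomes imply that cause was recorded at the calls. The sponsor should confirm this first.

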**Medication use**

Steroids (OCS):

- The number of courses per year (and total number of days) as recorded on the diary card. Each mention of use on a separate diary card indicates a course.
- The proportion receiving none vs. any during the trial as recorded on the diary card or in the phonecall data.

Steroids (ICS):

- Proportion starting ICS during the trial as recorded on the diary card or phonecall data (baseline data (T2) indicates whether child was on ICS at the start of the trial)

Salbutamol:

- Total number of puffs overall per episode of wheeze as recorded on the diary card
- Total number of puffs (Salbutamol use per year)

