### **Methods for withdrawals, loss to follow-up and missing data**

Those participants who withdraw and provide permission to use their data will be included in the analysis up to the point of withdrawal.

For the primary outcome phonecall data, at the time of writing (prior to unblinding) we have:

Full 12 months data on 1134/1347(84%)

29/1347 (2%) participants withdrew before the first 2 month phonecall and have no data collected as expected

12/1347 (0.9%) do not have any follow up data and this is being queried with the sites

Partial follow up data is available for 172 (13%). 44 of these participants did not formally withdraw from follow up. This is being queried with the sites

After data cleaning we expect the levels of missing data to improve. Due to these relatively low levels of missing data, and that the follow up time for each participant is to be included in the analysis no imputation of the missing data will be performed

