### **Primary analysis**

The primary analysis will be a Poisson regression model with the follow up time of each individual fitted as an exposure variable and with a random effect for individual to account for overdispersion.

The incident rate ratio (IRR) for the treatment effect and corresponding 95% confidence interval will be presented. An IRR of less than 1 indicates a benefit of Montelukast in reducing the rate of unscheduled medical attendance needed.

Assumption checks and actions to be taken if assumptions do not hold

The fit of the model will be compared to a model without a random effect using the likelihood ratio test, and the fit will be assessed using diagnostic plots (residuals versus fitted values), alternative distributions to the Poisson such as the Negative binomial or removal of the random effect shall be considered where necessary for improved fit.

Other analysis supporting the primary (inc. sensitivity analyses)

The primary analysis will be performed on the per-protocol population and using a CACE analysis.

It will be repeated replacing any stratification factors that were incorrectly defined at randomisation with the corrected values (see section 1.4).

It will be repeated with exclusion of 11 incorrectly randomised participants (see section 1.4).

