### **Secondary analysis**

The primary analysis will be repeated for each of the following secondary outcomes:

individual type of medical attendance: (hospital admission, hospital attendance (a&e), and GP visit)

Duration (in days) of hospital admission

Number of wheeze episodes

Duration of wheeze episode

The number of steroid (OCS) courses per year

The number of IMP courses per year

Time to event data will be summarised using Kaplan Meier plots. The treatment effect will be evaluated using a Cox regression model. The Hazard Ratio (HR) for the treatment effect and corresponding 95% confidence interval will be presented. A

HR of less than 1 indicates a benefit of Montelukast in reducing the time to first event.

first hospital admission

first hospital attendance (A&E)

first GP visit

first episode of wheeze

Binary outcomes will be analysed with logistic regression

proportion receiving no steroids (OCS) vs. any during the trial

Proportion starting steroids (ICS) during the trial

Assumption checks and actions to be taken is assumptions do not hold

The assumption of proportional hazards for the cox regression model will be checked using the methods proposed by Grambsch and Therneau. If this assumption is violated, alternative methods will be used.

See section 8.4 for Poisson regression assumption checks.

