**Number of:**  
**Wheeze episodes**  
**Cold episodes**  
**Days wheezing**  
**Returned used medication sachets**

**Duration of:**  
**Wheeze episodes (days)**  
**Hospital admission (days)**

---

Data are mean (SD)

 Data are analysed using Poisson regression with fixed effects for stratification factor and treatment group a random effect for individual to account for overdispersion with follow up time fitted as the exposure. Duration of each hospital admission is analysed using Poisson regression with fixed effects for stratification factor and treatment group a random effect for individual with follow up time fitted as the exposure.

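### Count models for diary-card outcomes name follow-up time as the exposure, although the SAP says diaries end when IMP stops

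*SAP*

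**What the plan says.** **Observation windows.** Derived and computed variables gives two. Attendance data run to 12 months or withdrawal from follow-up. Children with no cold or wheeze episode are censored at 12 months or "withdrawal from medication, as diary cards are not completed for those not taking IMP". The Withdrawals data items record withdrawal from treatment and from the trial as distinct events, with a date.

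**Count models.** The Primary analysis section specifies a Poisson model "with the follow up time of each individual fitted as an exposure variable". The Secondary analysis section then states: "The primary analysis will be repeated for each of the following secondary outcomes". Its list includes number of wheeze episodes and OCS courses. Footnote 1 to Appendix Table 4, which also covers cold episodes and days wheezing, specifies "a random effect for individual to account for overdispersion with follow up time fitted as the exposure". Footnote 1 to Appendix Table 6 says the same for OCS courses. No separate exposure is defined for diary data.

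**OCS courses.** Under Medication use the count comes from the diary card: "Each mention of use on a separate diary card indicates a course".

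**Yes/no outcomes.** Any OCS use and starting ICS are taken from the diary or the phone call. "Binary outcomes will be analysed with logistic regression", and footnote 2 to Table 6 lists only stratum and treatment as terms. The missing-data section gives two reasons for not imputing: missing data are relatively few, and "the follow up time for each participant is to be included in the analysis no imputation of the missing data will be performed".

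**The concern.** The Cox models and the count models draw on the same diaries but are given different observation windows. In the Cox models a child leaves the risk set when IMP stops. In the count models, read as written, the same child stays in the denominator until follow-up ends, although nothing more can enter the numerator. These children are not removed elsewhere: secondary outcomes are analysed by intention to treat, and only the per-protocol set drops those who discontinue IMP.

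The consequence is a rate that is too low in whichever arm stops IMP more often or earlier. Different stopping is plausible, since perceived lack of efficacy and adverse events are both listed as reasons for withdrawal. If placebo children stop more, montelukast looks worse than it is; if montelukast children stop more, it looks better. At stake are the secondary rate ratios for wheeze episodes, cold episodes, days wheezing and OCS courses.

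The yes/no outcomes raise a smaller, separate matter. A child seen for four months has less opportunity to record any use than one seen for twelve, and the logistic model treats them alike.

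**Working it through.** **Figures in the SAP.** The follow-up counts add up: 1134 + 29 + 12 + 172 = 1347. Partial phone follow-up is 172/1347 = 12.8%. These figures are pooled over arms and concern phone-call data. The SAP gives no share of children stopping IMP and no timing by arm, so the stopping figures below are assumptions.

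**One child.** IMP stops at month 4 and phone follow-up continues to month 12. Diaries cover 4 months and the denominator is 12, so 8/12 of the denominator cannot contain a diary event.

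**Arm level, no true effect.** Let w1 and w0 be the shares stopping IMP in the numerator and denominator arms, and f the fraction of the year with diaries among those who stop. The expected rate ratio with a full-year denominator is

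[1 − w1(1 − f)] / [1 − w0(1 − f)].

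With stopping at month 4, 1 − f = 8/12:

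- 5% vs 10%: 0.9667/0.9333 = 1.036 (0.966 with the arms reversed).
- 10% vs 20%: 0.9333/0.8667 = 1.077.
- Equal shares and timing: 1.00.

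Varying f from 0.25 to 0.75:

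| Stopping (montelukast vs placebo) | Null rate ratio |
|---|---|
| 10% vs 15% | 1.01 to 1.04 |
| 10% vs 20% | 1.03 to 1.09 |
| 10% vs 30% | 1.05 to 1.19 |
| 20% vs 10% | 0.92 to 0.97 |
| 30% vs 10% | 0.84 to 0.95 |

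**Effect on the test.** Simulation with 673 per arm, 1,000 trials per setting, true ratio 1, uniform stopping times and a negative binomial model. The first event rate uses the SAP's mean 0.76 and SD 1.22, so k = (1.22² − 0.76)/0.76² = 1.26. The second assumes 4 episodes a year with k = 0.7.

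| Events/year | Stopping | Full-year exposure: ratio, rejection | Diary-time exposure: ratio, rejection |
|---|---|---|---|
| 0.76 | 15% vs 15% | 1.004, 5.8% | 1.004, 5.1% |
| 0.76 | 10% vs 20% | 1.050, 8.7% | 0.996, 5.2% |
| 0.76 | 10% vs 30% | 1.114, 23.7% | 0.997, 5.8% |
| 4 | 15% vs 15% | 1.001, 7.0% | 1.001, 5.4% |
| 4 | 10% vs 20% | 1.061, 20.3% | 1.004, 3.9% |
| 4 | 10% vs 30% | 1.117, 54.9% | 1.000, 5.4% |

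Stopping here is unrelated to wheeze, so the table shows what the exposure variable alone can correct.

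**Yes/no outcomes.** With the same 0.76 and 1.22, the chance of any use by time t (in years) is 1 − (1 + k × 0.76 × t)^(−1/k). Suppose follow-up ends early in 10% vs 15%, an average of 12.5% and so close to the pooled 12.8%, with nothing recorded afterwards. The null odds ratio is then 1.01 to 1.06 for f from 0.75 down to 0.25. Equal loss gives 1.00.

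**The case against.** The best defence is that the SAP never says diary counts are divided by the full year. Follow-up time is not defined for diary outcomes, and an analyst who had read the censoring rule might end it at IMP withdrawal. That is fair as far as it goes: full follow-up is an inference, though a strong one. The primary model is reused unchanged, the table footnotes repeat its exposure, and the Data collection section describes total wheeze days as covering the follow-up period. A rule that has to be guessed is still a defect.

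The size may also be small. At 0.76 events a year with SD 1.22 and 673 per arm, the standard error of the log rate ratio is about √(2 × 1.22²/0.76²/673) = 0.088. A ratio of 1.036 (log 0.035) is then about 0.4 standard errors. This stands; larger imbalance or more frequent events make it matter more.

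A reader might infer several stronger things that the SAP does not support:

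- **That IMP withdrawal is the main threat to the yes/no outcomes.** Those also use phone-call records, which can continue after IMP stops. The clearer threat is incomplete follow-up.
- **That all 213 children without full data (1347 − 1134) would be coded as non-users.** That number includes 29 + 12 = 41 with no data at all, and nothing says they are coded that way. Of the 172 with partial data, 44 had not formally withdrawn and were being queried.
- **That an OCS course is counted twice when it spans two cards.** The period covered by one card is not stated.
- **That the sample size is compromised because it used OCS courses.** Those were external data serving as a proxy for attacks.
- **That ICS start ignores baseline use.** The outcome definition already points to baseline data on who was on ICS.

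**Conclusion.** The point holds as a conflict between a stated observation window and a stated model. It affects diary-only counts: wheeze episodes, cold episodes, days wheezing and diary-card OCS courses. The direction is clear: the arm with more or earlier IMP stopping gets a rate that is too low. The size cannot be determined from the SAP. Under the assumption of stopping at month 4 it is 1.036 for 5% vs 10% and 1.077 for 10% vs 20%, with no distortion under the null if stopping patterns are equal. It would be wrong to conclude that these results are biased; they are exposed to bias if stopping differs by arm.

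The primary outcome is not touched, because it comes solely from phone-call data.

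The secondary point is narrower. One of the two reasons for not imputing, that follow-up time is in the analysis, does not apply to the two logistic outcomes. The other reason, low missingness, remains. At most 12.8% had partial phone follow-up when the SAP was written, and improvement was expected after cleaning.

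**What to change.** 1. For diary-only counts, define the exposure as time from randomisation to the earliest of IMP withdrawal, withdrawal from follow-up or 12 months. This matches the censoring already set for time to first wheeze or cold. State it in Derived and computed variables and in the footnotes to Tables 4 and 6.
2. Keep OCS courses diary-only with this same exposure, so that numerator and denominator cover one window. Adding phone-reported courses from after IMP stopped, over diary time, would create the opposite bias. The listed phone-call medication items also include no dates for merging.
3. Report the number and timing of IMP withdrawals by arm. The new exposure does not remove bias if children stop because of their wheeze, so add a sensitivity analysis for informative stopping.
4. For any OCS use and ICS start, add an analysis that accounts for follow-up length, for example a complementary log-log model with log follow-up time as offset. It assumes a roughly constant rate of first use. Correct the reasoning on imputation for these two outcomes.

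The cost is SAP wording, one derived exposure variable and a few supporting analyses. Withdrawal type and date are already collected. The SAP says it was written before trial data were examined, so the change can be prespecified if made before unblinding.
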